Disease-induced fatigue that is manifested by physical or mental illness and / or is a consequence of treatments and medications is a common topic of research in disease management. Such fatigue can be managed by addressing medically treatable causes (15). However, many older people experience general fatigue with no specific known cause. This type of fatigue has been reported in 27-53% of community- dwelling older people worldwide (16). General fatigue is partly caused by age-related bio- physiological changes, such as reduced muscle strength and mass, leading to decreased muscle endurance. This, together with a gradual decline in cardiovascular and pulmonary functions also leads to a reduction in the maximal heart volume and to a decrease in the vital capacity and expiratory volume of older people. These changes predispose older people to reduce their rate of oxygen consumption during activities, and cause them to feel more fatigue when performing even mild daily activities (1). The general fatigue experienced by older people has been likened to a continuum between mild ‘tiredness’ and severe ‘exhaustion’ (17). Exhaustion (a severe level of fatigue) may not be relieved by rest, leading to a decreased capacity for everyday physical and mental activities (17). The terms ‘exhaustion’ and ‘fatigue’ are used interchangeably in most studies, and also in this proposal. Longitudinal studies have shown that older people with self-reported general fatigue have more restricted activities(3), poorer physical function, slower gait speed, and disability(4, 5), increased utilization of home-help and hospital services(6), and even a higher risk of mortality in the long term (i.e., 3-5 years)(18). In fact, exhaustion, together with unintentional weight loss, low levels of activity, a slow walking speed, and a decreased grip strength are the five phenotypes of frailty(7). This physiological state of increased vulnerability to stressors results from a decrease and possible dysregulation of reserves in multiple physiological / biologic systems (8, 19-21). Epidemiological studies have found that exhaustion is one of the most common characteristics exhibited in older people with frailty. A longitudinal study of 420 non-frail older women found that women with exhaustion were 3-5 times more likely to develop frailty seven years later (at which 80% of them developed frailty) when compared with those without exhaustion(2). The empirical evidence shows that general fatigue is prevalent among older people and can predict frailty and disability in the long term. This evidence raises the concern that a decrease in the production of energy or an inability to cope with an increased utilization of energy could be very much a part of the transition to a final common pathway of frailty and disability. Despite this, the management of fatigue has not yet received adequate attention in gerontological care (12).

Likelihood of exercise interventions in managing general fatigue among older people:

Studies investigating the effects of exercise interventions on the general fatigue experienced by older people are currently lacking (15). However, the evidence suggests that patients with disease-induced fatigue feel less exhausted and more energetic as a result of engaging in regular exercise. Fortunately, recent studies have shown that among people who consistently feel exhausted, those who are willing to gradually exceed their perceived energy limits and recondition their bodies by

participating in exercise programmes gradually experience less fatigue (11, 25, 26). Although the causal pathways for different types of fatigue are not the same, the self-perpetuating vicious cycle of fatigue explained under the decondition model is similar between sufferers with different types of fatigue (27). Additionally, exercise targeting the muscle strength, mobility (28, 29), and cardio-respiratory (30) fitness of older people can improve functional capacity, and may improve their perception and condition of fatigue (31).

Rationale for combining exercise therapy with a behavioural change intervention

Older people can only obtain all of the benefits of exercise after they have engaged in regular exercise at their individual attainable level for 3-5 months (32). Over-sensitivity to physical responses such as mild muscle tiredness after exercise may have led to the avoidance of physical activity; thus, high dropout rates were reported among participants with fatigue in the exercise groups (25, 26). A review reported that the dropout rate can be up to 25% when exercise interventions are implemented among older people with various health problems. As pre-existing multiple health problems (such as pain and fatigue) are common among older people, it is not surprising that fatigue was a common cause of their non-adherence or withdrawal in controlled trials of exercise programmes (15, 24). Nevertheless, if prescribed exercise levels are beyond their physical and psychological capabilities, this may also lead to exhaustion, causing them to drop out. To overcome this problem, it is suggested that behavioural change enhancement strategies focusing on enhancing motivation be given alongside an exercise programme (22, 23, 26, 33). The Health Action Process Approach (HAPA) model divides the process of behavioural change into two phases: motivation and volition (34). The motivation phase refers to the goal initiation phase. ‘Self-efficacy’, ‘outcome expectancies’, and ‘increased risk awareness’ are the three attributes that motivate individuals to form an intention / goal to change their unhealthy lifestyle for a healthy lifestyle. The volition phase refers to the process of implementing intentions into actual behaviour through careful planning and action execution (Appendix I: Figure of HAPA). The empirical evidence shows that the HAPA model can be effectively used as a conceptual framework to design concrete strategies to motivate behavioural changes. Used alongside exercise interventions, these strategies can promote adherence to exercise regimes among those undergoing orthopedic rehabilitation (35) and cardiac rehabilitation (36, 37), and among older patients with sedentary lifestyles (38).

B. Research plan and methodology (Appendix 1: Research flowchart)

Aim: The aims of this study are to investigate the effects of an individualized exercise programme with and without BCE strategies for community-dwelling frail older people with general fatigue, so as to reduce their fatigue and improve their physical endurance, exercise self-efficacy, and habitual physical activity, while reducing their symptoms of frailty.

Design: A single-blinded three-arm cluster-RCT is proposed to examine the effect of a 16-week individualized exercise programme with or without BCE strategies for frail older people with general fatigue. To explore the way in which the combined intervention will be implemented (42), a focus group with 30 COMB participants (4-6 per group) will be interviewed by a trained research assistant (RA) to identify the strengths, limitations, and therapeutic components of the combined intervention from their perspectives.

Subjects and Settings: Eligibility criteria for district community health centres are those that are funded by the Hong Kong (HK) government and under the supervision of the Social and Welfare Department of HK, and thus that meet a specific set of standard regulations and criteria on environment and practices. All twelve community centres, which provide similar types of community care and social support services for community dwelling older people, have been invited by a convenience method to work as collaborators in this study. The target population of this study are community-dwelling frail older people with general fatigue with a nonspecific cause who will be recruited through the community centres.

Sample size estimation, recruitment procedures, random allocation, and allocation concealment:
The changes in the mean fatigue scores were -0.58, -5.16, and -2.66 for the control, EXER, and COMB groups respectively, from pre-test to immediately post-intervention in the pilot study. The Cohen's d effect sizes for the EXER and COMB groups were 0.51 and 0.23, respectively; whereas the overall effect size was 0.21. As no similar cluster-RCT has been reported in the literature and the cause of general fatigue is heterogeneous, we assumed that an intra-correlation coefficient would be low (0.01) within each cluster (43). Based on an effect size of 0.21 in the pilot study, and four clusters (community centres) per group with an intraclass correlation of 0.01, a significance level (α) of 0.05, and a power ($1-\beta$) of 0.8 for a two-sided test, the sample size was calculated to be 76 participants per group according to NCSS PASS 14. For a long-term follow-up of 12 months, 285 participants (95 per group) will be recruited after considering an attrition rate of 20%. Using computer-generated random numbers, a biostatistician not affiliated with this study will randomize the centres into either: control, EXER, or COMB. The randomization will be stratified based on the size of the centres. Small-medium centres will be defined as those with < 800 ($n=9$) clients, whereas those with > 800 clients will be defined as large ($n=3$). The number of participants recruited in each centre will be in proportion to the size of the centre (i.e., the total number of clients). We estimate that about 25-50% (4, 16, 44) of the 8,710 members of these centres will be eligible to participate. To avoid selection biases, the allocation to the study groups will be concealed from the researchers until the recruitment of the sample and measurement of the baseline have been completed (please refer to the item 13 in this application for details of the collaborators).

The Inclusion Criteria are: 1) community-dwelling older people aged > 70 years; 2) able to communicate in Cantonese to ensure that they understand our instructions; 3) able to walk with or without an assistive device and able to complete the Time Up and Go (TUG) test with no specific cutoff point to ensure that their mobility and balance is good enough to join the exercise training; and 4) in a frail state with exhaustion as determined using the Fried Frailty Index (FFI)(7), including: i) an unintentional loss of 10% of body weight in the past year; ii) exhaustion: by answering 'Yes' to either 'I felt that everything I did was an effort', or 'I could not get going in the last week'; iii) a slow walk time: with an average walking speed in the lowest quintile stratified by median body height; iv) reduced grip strength: with maximal grip strength in the lowest quintile stratified by body mass index quartile; and v) the Physical Activity Scale for the Elderly-Chinese (PASE-C) score in the lowest quintile (i.e., < 30 for men and < 27.7 for women). The presence of > 3 items indicates frailty, and one criterion indicates that they suffer from exhaustion.

Sample selection for the focus group: Purposive samples of 30 participants (31.5%) from the COMB group will be selected to join in one interview (if needed, a second interview will be organized for follow-up questions and clarifications). To obtain a wide variety of opinions, six focus groups interviews (4-6 participants per group) will be conducted with 10 participants who had a significant positive reduction in their fatigue scores of > 5 out 20 total score, 10 with a minimal reduction in their fatigue scores of between 1-5, and 10 with no or negative changes on their fatigue score between the baseline and post-test 1 measurement.

Interventions: (*Appendix II:* Overview of the combined intervention) A 16-week programme with a combination of exercise and the BCE programme (plus two booster BCE sessions will be held at 2 and 6 months after the programme) will be arranged for the COMB group. Another 16-week programme with a combination of exercise and health talks will be arranged for the EXER group, whereas participants in the control group will attend only the health talks with no other intervention. Two added health talks will be arranged at 2 and 6 months after the programme for the EXER and the control groups. To control the group and social interaction effects of the BCE programme for the COMB group, the number and timing of the health talks for the other two groups will be similar to those in the BCE sessions. All face-to-face sessions will have < 10 participants to maintain good interactions between the participants and the exercise instructor / BCE facilitator/ health talk speakers.

The behavioural change enhancement (BCE) programme in the COMB group (Appendix III: BCE programme protocol) aimed at motivating the participants to develop the intention to actively manage their fatigue; and to encourage them to gradually exceed the perceived limits of their energy and to recondition their bodies by participating in exercise according to their individual exercise regimens. The BCE programme was designed based on the HAPA model and was piloted by the PI

(14). It consists of three phases with six face-to face one-hour sessions plus two booster BCE sessions at 2 and 6 months. The first three weekly sessions will be arranged during the ‘goal initiation’ and ‘planning’ phases. The remaining three sessions and two booster sessions will be offered once per month in weeks 4, 8, and 12 during the programme; and at 2 and 6 months after the programme during the ‘action execution’ phase.

Exercise intervention in the EXER and the COMB groups: A weekly 45-60 minute centre-based exercise programme, which designed according to the American Heart Association’s recommendations on exercise for older people (48), will be arranged from weeks 4-16 during the execution phase. This programme will consist of balance training, such as sideways walking (15-20 minutes); resistance exercises, such as using resistance bands to improve muscle strength in both the upper and lower limbs (10-20 minutes); aerobics training, such as walking (10 minutes) and with 10 minutes of warm-up and cool-down exercises at the beginning and at the end. All participants will receive circuit training with set exercises, but the dosage of different components will be tailor-made for each participant based on his/her physical conditions. The first assessment will be in week 4 (i.e., the first week of the exercise programme), and subsequent monthly assessments will be held in weeks 8 and 12 by a physiotherapist. The dosage of exercises will gradually increase by increasing the number of repetitions, the duration of the exercises, and also by using progressively heavier wrist and ankle weights maintained at approximately 12-14 on the Borg Rate of Perceived Exertion Scale(28, 49), based on the participants’ progress. The dosage of exercise recommended to each participant by the physiotherapist will be recorded. Demonstrations and return demonstrations will be performed during the training to ensure that the participants are able to do the exercises properly. A compact disc and a pamphlet describing the different types of exercises used in this programme will be disseminated to all participants to encourage them to continually practice their exercises at home for approximately 30 minutes at least 3 times per week. Although this set of exercises was used in the pilot study with no reports of adverse effects, safety guidelines on exercise for older people will be discussed with all of the participants.

The Control Condition: Participants in the control and EXER groups will attend centre-based health talks on the management of different health issues with the exception of fatigue. Another RA, who will not be involved in other procedures of this study, will run the health talks.

Instruments and Measures

Participants will be assessed on a variety of outcomes (described below) at week 8 (T1 at mid-term programme), 1 week (T2 immediate effect), 6 and 12 months after the programme (T3 and T4), which will be compared with the baseline assessment (T0). All assessments will be carried out by a part-time RA, regarded as an independent assessor, who will be blinded to the group assignments.

Socio-demographic data: The following data will be collected: 1) age, gender, marital status,

exercise habits, living conditions, and level of education, 2) the participants' health-related information, including cognitive status and medications. Additionally, their levels of comorbidity will be assessed using the Chinese version of the Charlson comorbidity index (C-CCI). The C-CCI score is the sum of the comorbidity and age scores, in which scores of 0, 1-2, 3-4, and > 5 represent the comorbidity level as none, low, medium, and high, respectively⁵⁰. The health services utilization of the parents in the past 12 months and during the study period, such as the number, duration, and causes of hospital admissions and scheduled/non-scheduled clinical visits, will be collected during each measurement time point and will be treated as a co-variate if needed.

Primary outcome measurement: Fatigue will be assessed using the 20-item Chinese Multidimensional Fatigue Inventory (CMFI-20)⁽⁵¹⁾. This scale was validated among 385 local cancer patients. A factor analysis revealed that it contains three factors (namely, physical, mental, and spiritual) with a factor loading ranging from 0.52 to 0.75. The Cronbach's α was between 0.7 and 0.8 for three domains and the total of the CMFI-20 score. It supports the view that the CMFI-20 is a reliable and valid instrument.

Secondary outcome measurements

Physical Endurance will be evaluated using different physical tests. First, the participants' lower-limb and upper-limb strength will be assessed using a 30-second chair stand test⁽⁵²⁾ and a handheld Jamar Hydraulic Hand Dynamometer⁽⁵³⁾, respectively. Their mobility and overall physical endurance will be assessed through the TUG test and by their gait speed (6-m walk).

Exercise Self-efficacy: The participants' self-confidence in their ability to exercise in a variety of circumstances (e.g., when feeling tired) will be assessed using the 9-item Chinese Self-Efficacy for Exercise scale (CSEE) (54, 46). The CSEE was validated on 192 Chinese older people. Discriminant validity was shown by the CSEE total score, which significantly differentiated between individuals with or without regular exercise. The Cronbach's α was 0.75, which showed an acceptable level of internal consistency.

Frailty status: This will be assessed based on the FFI mentioned in the sample inclusion criteria (7).

Physical activity level will be assessed using the 10-item PASE-C⁽⁵⁵⁾ to measure self-reported occupational, household, and leisure activities for the last week. Its total score is calculated by multiplying the amount of time spent in each activity (hours / week) by the weight of the pre-set item. PASE-C has been shown across different studies to be a reliable and valid instrument (56, 57).

Depressive Mood: A 15-item C-GDS⁴⁵ will be used on all participants to measure the exhibition of depressive symptoms. The scores '0 to 4', '5 to 9', and '10 to 15' indicate 'normal', 'mild', and 'moderate to severe' depressive mood, respectively. The C-GDS is commonly used in both clinical and research settings, and has shown good reliability and validity^{45, 58}.

Formative or Process Evaluation is aimed at exploring the COMB group participants' perceptions of the strengths and limitations of the intervention. The data will provide valuable insights for the research team to realize / identify the positive components of the combined intervention and the barriers and difficulties faced by the participants in attending/adhering to the intervention.

Procedures: (*Appendix IV*: Detailed Ethical Considerations; *Appendix V*: CONSORT diagram of the Cluster RCT) Ethical and access approval will be obtained from the Ethics Review Committee of The University and study venues, respectively. Potential participants will be referred to the research team by the collaborators. An RA will screen all potential participants for their eligibility to participate in this study. Written informed consent will then be obtained from all of the participants, to whom all aspects of the study will be explained and questions answered. They will then be interviewed to obtain their health-socio-demographic data, and baseline assessment. After that, the twelve community centres will be randomized to either the control, EXER, or COBM group. Participants from each centre will be placed into their centre's corresponding group to avoid 'contamination' effects across participants. At the mid-term programme, 1 week, 6 months, and 12 months post-intervention, an independent assessor who is blinded to the group allocations will assess the participants' outcomes, which will be compared with the baseline assessment. Focus group interviews will be conducted by the trained RA after the first post-test 1 (one-week post-intervention). Purposive samples of 30 participants from the COMB group will be selected to take part in one interview (4-6 per group). They will be asked to comment on their experiences and (dis)satisfaction regarding the programme, perceptions of its positive/negative aspects, concerns and difficulties in participating and adhering to the programme, and ways of improving the intervention. A semi-structured interview guide will be developed for these interviews, which will be conducted in Cantonese, and all interviews will be audio-recorded for content analysis. Examples of interview questions include: "What are your opinions and comments on your participation in the programme?" and "What are your changes and / or difficulties in adherence to the exercise regimen during and after the 16-week programme?"

Intervention fidelity and RA training: The PI will train an RA on how to use all of the outcome instruments with reference to the latest user guidelines for the instruments, so that the RA can act as an independent outcome assessor. The RA will practise using all of the instruments, with clinical vignettes and on-site practise. The inter-/intra-rater reliabilities will be evaluated by the intra-class correlations (ICC). Acceptable levels of reliability (ICC > 0.9) will be established by comparing the scores rated by the assessor and the PI prior to the start of the study, and checking them on a monthly basis throughout the data collection period. These procedures are to ensure that quality assessments are performed as intended. The protocols of the exercise and BCE programmes have been developed and tested in the pilot study (14). They will be used to guide the implementation of all interventions in different sub-groups to ensure standardization throughout the study. The pre-intervention practice of the BCE facilitator and the exercise instructor will be supervised by the research team on one or two small groups of older adults with general fatigue. All BCE and exercise sessions must follow the programme protocol and will be run by the same facilitator/exercise instructor to ensure intervention consistency. Intervention fidelity checking will be conducted in the training period and then monthly to bimonthly during the intervention period based on the BCE facilitation/exercise checklist.

Achieving a fidelity rate of > 90% will be considered acceptable based on the recommendations of the NIH Behaviour Change Consortium (59). This is to ensure that all of the interventions are executed by the exercise instructor or the BCE facilitator as intended. Monthly quality control meetings with all research personnel (the exercise instructor, BCE facilitator, and RAs) will be arranged to evaluate their instruction/facilitation skills in this study.

References:

1. Avlund K. Fatigue in older adults: an early indicator of the aging process? *Aging Clin Exp Res.* 2010; 22(2): 100-15.
2. Xue Q-L, Bandeen-Roche K, Varadhan R, Zhou J, Fried LP. Initial manifestations of frailty criteria and the development of frailty phenotype in the women's health and aging study II. *J Gerontol A Biol Sci Med Sci.* 2008; 63(9): 984-90.

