SPSS version 23.0 will be used to analyse the data. An intention-to-treat analysis will be adopted. Descriptive statistics will be generated for the demographic data. Normality assumptions for the variables will be checked. The baseline characteristics of the participants in the three groups will be compared using ANOVA for the continuous variables, a chi-square test for the categorical variables, and the Kruskal-Wallis test for the ordinal variables. Mixed-effects modelling will be used to measure changes in the outcome assessments across the mid-term programme (at week 8) and the three post-tests (1 week, 6 months, and 12 months after the intervention) among the three groups, followed by the Helmert contrasts test (if any results are found to be significant)(60). Another mixed-effects modelling approach will be used to measure the participants' attendance rate in the weekly exercise sessions and their adherence to the home exercise during the programme and the follow-up period between the EXER and the COMB groups. Any pre-test outcome scores, demographic information, data on health conditions, comorbidity index, health service utilization, dosages of exercise recommended by the physiotherapist, and participation in other exercise programmes during the study period, indicating significant differences between groups, will be treated as co-variates as needed. Multiple imputations will be adopted to manage missing data. A p-value of < 0.05 will be considered statistically significant. Content analysis will be used to analyse the interview data⁶¹. All audio-taped interviews will be transcribed into Chinese by the RA and the transcriptions will be checked for accuracy by the PI using QSR NVivo 11. The revised transcripts will be coded independently by two (Chinese-speaking) Co-Is. The research team will then discuss the identified codes and come to an agreement on them, grouping them into main (sub)categories with the support of verbatim data. The (sub)categories will then be condensed and/or re-organized when deemed necessary. The research team will examine them for consistency, reach a consensus about their meaning and structure, and devise a list of finalized categories. A set of (sub)categories with supporting verbatim data will finally be generated to identify the major strengths and limitations of the combined intervention to come up with improvements for its future use.

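### The sample size rests on one overall three-group effect driven almost wholly by EXER v control, so the stated 80% power says nothing about COMB v EXER, the only contrast that isolates BCE

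*Protocol*

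**What the plan says.** The Protocol's Aim is to "investigate the effects of an individualized exercise programme with and without BCE strategies". There are three arms. COMB receives exercise plus BCE, EXER receives exercise plus health talks, and control receives health talks only. The Interventions section keeps the talks similar to the BCE sessions in number and timing, to control for group and social contact.

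The sample size section gives the pilot results: "The changes in the mean fatigue scores were -0.58, -5.16, and -2.66 for the control, EXER, and COMB groups respectively", measured from pre-test to immediately after the intervention. It then says "The Cohen's d effect sizes for the EXER and COMB groups were 0.51 and 0.23, respectively; whereas the overall effect size was 0.21". The calculation uses only the last of these: "Based on an effect size of 0.21 in the pilot study", with "four clusters (community centres) per group with an intraclass correlation of 0.01", "a significance level (α) of 0.05", and a power "of 0.8 for a two-sided test, the sample size was calculated to be 76 participants per group according to NCSS PASS 14". Allowing for 20% attrition, 95 per group (285 in all) are to be recruited. No power is given for any comparison between two arms.

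The SAP plans a three-group mixed-effects model across the mid-programme assessment and three post-tests, "followed by the Helmert contrasts test (if any results are found to be significant". It does not give the group order for those contrasts. Neither document names a primary time point or a primary contrast.

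**The concern.** The question the trial is built around is exercise with BCE against exercise without it. The matched health talks exist so that this comparison is clean. An overall three-group effect can be large while the arm carrying BCE contributes almost nothing to it, and the pilot shows that pattern. Power for the overall test then does not carry over to the comparison that matters.

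The analysis rule adds to this. Contrasts are run only after a significant overall result, and at the pilot values that result would mainly reflect EXER v control, the one pair without BCE. Depending on the Helmert order, COMB v EXER may not even be one of the contrasts. The trial could finish without a planned estimate of what BCE adds, or with a non-significant one that is hard to interpret because its precision was never stated.

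**Working it through.** **Inputs.** From the Protocol's sample size section: pilot mean changes of -0.58 (control), -5.16 (EXER) and -2.66 (COMB); d = 0.51 and 0.23; overall effect 0.21; 76 analysed per group; four centres per group; ICC 0.01; two-sided 5%. The SD of change is not printed and is derived in step 1. Nineteen participants per centre (76/4) is an average.

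**1. Implied SD.** EXER v control: 5.16 - 0.58 = 4.58, and 4.58/0.51 = 8.98. COMB v control: 2.66 - 0.58 = 2.08, and 2.08/0.23 = 9.04. The two agree, so both d values are differences from control with an SD of about 9.

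**2. Reproducing 0.21.** The grand mean is -2.80. Deviations are 2.22 (control), -2.36 (EXER) and 0.14 (COMB); their squares are 4.928, 5.570 and 0.020, summing to 10.518. Cohen's f = sqrt(10.518/3)/9 = 1.872/9 = 0.208. The printed 0.21 is therefore a three-group f.

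**3. Reproducing 76.** One-way three-group ANOVA, noncentral F with noncentrality 3n × f²/DEFF. With no clustering, 80% power needs 76 per group at f = 0.208, or 74 at f = 0.21. Read instead as a two-group d, 0.21 would need 356 per group. So the stated N fits the overall test, and fits it with the ICC at 0.

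**4. Where the effect comes from.** Shares of the sum of squares are 46.9% (control), 53.0% (EXER) and 0.2% (COMB). As a single contrast, EXER v control carries (4.58²/2)/10.518 = 99.7%.

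**5. Power by comparison.** Design effect = 1 + (19 - 1) × 0.01 = 1.18. For a pair, the standard error in SD units is sqrt(1.18 × 2/76) = 0.176. For control v the mean of both exercise arms it is sqrt(1.18 × (1/76 + 1/152)) = 0.153. Noncentrality is the effect divided by the standard error. Results are for a noncentral t on 225 individual df (a normal approximation agrees within a point) and on 9 between-centre df (12 centres less 3 groups).

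| Comparison | Effect (SD) | Noncentrality | Power, individual df | Power, 9 df |
|---|---|---|---|---|
| EXER v control | 0.51 | 2.89 | 82% | 73% |
| Control v mean of EXER and COMB | 3.33/9 = 0.37 | 2.42 | 67-68% | 58% |
| COMB v control | 0.23 | 1.31 | 26% | 22% |
| COMB v EXER | 2.50/9 = 0.278 | 1.58 | 35% | 29% |

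With ICC 0 the three pairwise figures are 88%, 29% and 40% (individual df).

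**6. Direction.** COMB improved 2.50 points less than EXER in the pilot, so the 35% is the chance of finding COMB worse. The chance of a significant result favouring COMB is Φ(-1.96 - 1.58), about 0.02%.

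**7. Overall test on the same basis.** At 76 per group and f = 0.208-0.21, power is 80-81% with ICC 0, 73-74% with ICC 0.01, and 58-59% with ICC 0.01 on 9 df.

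**8. Detectable difference.** At 76 per group and ICC 0.01, 80% power for a pair needs about 0.50 SD (4.5 points), or about 0.56 SD (5.0 points) on 9 df. The pilot COMB v control difference is 2.08 points.

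**The case against.** The strongest reply is that nothing is miscalculated or concealed here. The Protocol labels 0.21 as overall, prints both arm-level d values beside it, and claims 80% for no pair. Sizing on the overall test also matches an SAP that starts from a three-group model. This stands. A reader might infer that the plan promises 80% for the BCE comparison, or that the sum is wrong on this point. The documents support neither, and the issue is what the stated power leaves unsaid.

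Other limits also stand:

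- COMB v control tests exercise plus BCE, not BCE. With Helmert order control, EXER, COMB, it would not be a planned contrast; the two would be control v both exercise arms and EXER v COMB.
- The 35% could be taken as power to show that BCE helps. It is the reverse.
- The figures are for one unadjusted visit, whereas the SAP plans repeated measures with covariates as needed. Assuming a correlation of 0.3-0.7, baseline adjustment at one visit gives about 29-37% for COMB v control and 40-50% for COMB v EXER. Averaging four visits with a constant effect gives about 47-70% and 63-85%, or 40-61% and 53-76% on 9 df. Only the top of one of these ranges passes 80%, and the Protocol does not size the trial that way. Still, one cannot say that a non-significant result is to be expected under the planned model.
- It is tempting to say the trial has little power for anything involving BCE. BCE is justified largely through adherence, and the SAP has a separate EXER v COMB adherence model. Pilot fatigue scores say nothing about power there.
- The SAP does not say that a non-significant contrast will be reported as no effect. That is a risk to guard against, not a stated intention.

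What the reply does not answer is that the contrasts depend on an overall result dominated by EXER v control, and that no precision is stated for the with-and-without-BCE comparison in the Aim.

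**Conclusion.** The point holds as one of design and reporting. The 80% belongs to an overall three-group test whose effect is 99.7% EXER v control, and it gives no information on COMB v EXER. On the plan's own pilot values, for fatigue change at one visit without adjustment, power is about 35% for COMB v EXER (29% on 9 df), in the direction of COMB being worse, against 82% (73%) for EXER v control.

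This rests on a derived SD of about 9, 76 analysed per group, ICC 0.01 and equal centre sizes. It also takes the pilot effects as true, because the plan chose them as its basis; they are uncertain. The longitudinal model could raise power by an amount the documents do not allow to be fixed. The conclusion that the 80% does not transfer would hold even if 76 per group did give 80% for the overall test. That the overall figure itself drops to 73-74% at the stated ICC is a separate matter, relevant here only because power figures set side by side must share one clustering assumption.

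**What to change.** Keep N.

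1. **Protocol, sample size section.** Say that 0.21 is the three-group f and that the stated power refers to the overall test. Give that power on the same clustering assumption as the rest: about 73-74% at ICC 0.01, or 58-59% on 9 df, with 80-81% only at ICC 0. Then list power for each comparison as in the working table, with its direction and the single-visit, unadjusted assumption. Note that the COMB v EXER figure is for a difference favouring EXER. Add the detectable pairwise difference of about 0.50-0.56 SD.
2. **SAP.** State the order of the Helmert contrasts. Commit to reporting COMB v EXER, and COMB v control, as differences with 95% confidence intervals whether or not the overall test is significant. State that a non-significant COMB v EXER result will not be read as evidence that BCE has no effect.

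The cost is wording only, with no extra participants, visits or procedures. The downside is a less favourable stated power.
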